7.3.2 Outcomes of interest

Outcomes of interest will be identified using the event-specific codes based on the coding system(s) used in the database(s) of interest (e.g. READ, International Classification of Diseases, 9th or 10th revision [ICD-9, or ICD-10], International Classification of Primary Care [ICPC]). Laboratory values will in general only be used to verify the certainty of a diagnosis, which may be used in sensitivity analyses (e.g. any case, laboratory confirmed cases only). Cases will not be identified based on using laboratory data alone to avoid inclusion of asymptomatic cases that were coincidentally detected because of screening that happened for other purposes.

Suggested terms that will be included in the mapping are listed in Annex 3 [Section 12.3.2](#). Narrative searches for identification of cases will be limited to PHARMO as free text does not add value or is absent/unavailable in the other databases.

7.3.2.1 Myotoxicity

Myotoxicity is defined as myalgia (muscle pain without evidence of raised CK), myositis (muscle symptoms with raised CK, typically < 10-times ULN), rhabdomyolysis (muscle symptoms with markedly raised CK, typically > 10-times ULN). Since not all of the database may systematically record all CK levels, we will not look at asymptomatic CK increases. These conditions will be identified using event-specific codes and laboratory measurements where available. Based on the publication by [Wiley et al \(2015\)](#), which made a systematic assessment of different phenotyping algorithms using US electronic medical record (EMR) data, the best performance is a combined approach of codes, laboratory measurements and textual searches. However, this may not be possible in all databases or applicable to EU data. Database specific algorithms will be developed. [Table 7-2](#) shows the components that may be used for each of the databases.

For individual terms to identify cases with myotoxicity, see [Annex 12.3.2.1](#).

Validation will be performed for all potential cases in the databases that allow for this and have not yet validated these outcomes before. We will also assess the number of potentially

missed cases that were asymptomatic but had raised CK levels, to assess the potential impact on the study results.

Table 7-2 Components for the identification of myotoxicity by database

	Database (country)				
	PHARMO (NL)	HSD (IT)	Aarhus (DK)	CPRD (UK)	SIDIAP (ES)
Codes	ICPC/ICD-10	ICD-9	ICD-10	READ	ICD-9/10
Laboratory (CK)	Yes	Yes	Yes	Yes	Yes
Text / symptoms	Yes	No	No	No	No

CK = creatine kinase; CPRD = Clinical Practice Research Datalink; DK = Denmark; ES = Spain; HSD = Health Search CSD Longitudinal Patient Database; ICD = International Classification of Diseases; ICPC = International Classification of Primary Care; IT = Italy; NL = the Netherlands; SIDIAP = Sistema d'Informació per al Desenvolupament de la Investigació en Atenció Primària; UK = United Kingdom

Note: details on databases, see [Section 7.4](#)

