7.3.2.2 Hepatotoxicity

Based on the level of elevation of transaminases or alkaline phosphatase (ALP) and the ratio (R) of elevation of baseline ALT to baseline ALP (ALT/ULN)/(ALP/ULN), drug-induced liver injury (DILI) is classified as either hepatocellular, cholestatic or mixed types (hepatocellular DILI: ALT \geq 3-times ULN and R \geq 5; cholestatic DILI: ALP \geq 2-times ULN and R \leq 2; mixed DILI: ALT > 3-times ULN and ALP > 2-times ULN and R > 2-times < 5-times ([Benichou 1990](#), [Devarbhavi 2012](#)). Not all the databases will allow for classification of the type of liver injury since ALT and ALP may not be available. Database specific algorithms based on codes, values and natural language processing (NLP) will be developed in line with the work done by [Overby et al \(2013\)](#) in the USA and [Afzal et al \(2013\)](#) in the Netherlands, where they explored various definitions of liver injury in electronic health care databases. [Table 7-3](#) shows the components that may be used for each of the databases. Viral hepatitis will be excluded from the cases.

For individual terms to identify cases with hepatotoxicity, see Annex 3 [Section 12.3.2.2](#).

Validation will be performed for all potential cases in the databases that allow for this and have not yet validated these outcomes.

Table 7-3 Components for the identification of hepatotoxicity by database

	Database (country)				
	PHARMO (NL)	HSD (IT)	Aarhus (DK)	CPRD (UK)	SIDIAP (ES)
Codes	ICPC/ICD-10	ICD-9	ICD-10	READ	ICD-9/10
Laboratory (ALT/ALP)	Yes	Yes	Yes	Yes	Yes
Text / symptoms	Yes	No	No	No	No

ALT = alanine aminotransferase; ALP = alkaline phosphatase; CPRD = Clinical Practice Research Datalink; DK = Denmark; ES = Spain; HSD = Health Search CSD Longitudinal Patient Database; ICD = International Classification of Diseases; ICPC = International Classification of Primary Care; IT = Italy; NL = the Netherlands; SIDIAP = Sistema d'Informació per al Desenvolupament de la Investigació en Atenció Primària; UK = United Kingdom

Note: details on databases, see [Section 7.4](#)

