7.3.2.3 Acute pancreatitis

Acute pancreatitis is characterized by the onset of parenchymal and peripancreatic fat necrosis with associated inflammation in a previously healthy individual.

Acute pancreatitis describes an acute inflammatory process of the pancreas that rapidly depletes intravascular water and, if unchecked, promotes regional inflammation. Commonly accepted criteria for a clinical diagnosis of acute pancreatitis necessitate the presence of 2 of the 3 following features: serum amylase and lipase elevated at least 3-times ULN; characteristic epigastric abdominal pain; and typical radiologic features as found on computed tomography (CT), magnetic resonance imaging (MRI), or transabdominal ultrasound (US) ([Frossard 2008](#)). Acute pancreatitis has been investigated in several European multicenter database studies such as EU-ADR and SAFEGUARD, and the algorithms for identification of acute pancreatitis and the validity will be obtained from these consortia.

[Table 7-4](#) shows the components that may be used for each of the databases.

For individual terms to identify cases with acute pancreatitis, see Annex 3 [Section 12.3.2.3](#).

Validation will be performed for all potential cases in the databases that allow for this and have not yet validated these outcomes.

Table 7-4 Components for the identification of acute pancreatitis by database

	Database (country)				
	PHARMO (NL)	HSD (IT)	Aarhus (DK)	CPRD (UK)	SIDIAP (ES)
Codes	ICPC/ICD-10	ICD-9	ICD-10	READ	ICD-9/10
Laboratory (amylase/lipase)	Yes	Yes	Yes	Yes	Yes
Text / symptoms	Yes	No	No	No	No

CPRD = Clinical Practice Research Datalink; DK = Denmark; HSD = Health Search CSD Longitudinal Patient Database; ES = Spain; ICD = International Classification of Diseases; ICPC = International Classification of Primary Care; IT = Italy; NL = the Netherlands SIDIAP = Sistema d'Informació per al Desenvolupament de la Investigació en Atenció Primària; UK = United Kingdom

Note: details on databases, see [Section 7.4](#)

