7.7.2 Final analysis

The final analysis based on validated cases will be conducted at the end of the study (after reaching the necessary number of cases) and is expected to be submitted in Q2 2020.

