7.9 Limitations of the research methods

The limitations of this study will be mainly due to the availability and level of detail of data. Not all potential confounders (e.g. life style factors such as smoking and alcohol use; or body mass index [BMI] which is a very dynamic variable and which is not well recorded or not recorded at all) are contained in (all) databases, this may lead to residual confounding.

Information on the prescribed dose and duration of a prescription is not contained in all databases and has to be estimated, which might lead to some misclassification of exposure, however, we do capture recency of exposure and can explore the effects of dose in PHARMO and CPRD which will allow us to assess the extent of this effect. Since LCZ696 may be prescribed by specialists initially we may misclassify exposure if it is not recorded in the databases. This would attenuate an effect since it is likely to be non-differential; a sensitivity analysis will be planned to address this.

All of the databases, apart from the Aarhus University Prescription Database and PHARMO, have information on prescription only and not on dispensing. None has information on actual drug intake. This implies that we do not know whether the patient actually took the drug – however, this may be non-differential leading to underestimation of risk.

Misclassification of endpoints as well as confounders is possible. For the different databases that will be used, validation studies have shown that coding is reliable in the databases and that these databases are suitable for pharmacoepidemiological research. For those databases where free text is available (PHARMO, HSD, CPRD and SIDIAP), validation of endpoints will be conducted and comparison of incidence rates of endpoints among databases in the quality run will allow checking for internal and external validity. Laboratory measurements will be needed for case finding/validation and the availability of these data will vary across the databases. The amount of misclassification of the outcome may differ between databases due to differences in availability of validation data or laboratory confirmations. However, since cases and controls are sampled and analyzed within the same database, misclassification will be similar for matched cases and controls in the same database. Bias due to misclassification of the outcomes may just differ between the databases.

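### The final analysis is promised on validated cases, but the validation rules leave some databases contributing cases that nobody confirms in this study

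*Protocol*

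**What the plan says.** The protocol describes case validation in four places.

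- **7.3.2.1 to 7.3.2.3 (outcome definitions).** For myotoxicity, "Validation will be performed for all potential cases in the databases that allow for this and have not yet validated these outcomes before". Hepatotoxicity has the same rule, "Validation will be performed for all potential cases in the databases that allow for this and have not yet validated these outcomes", and so does acute pancreatitis. For pancreatitis the protocol adds that "the algorithms for identification of acute pancreatitis and the validity will be obtained from these consortia", meaning earlier multi-database projects.
- **7.7.2 (which cases are analysed).** "The final analysis based on validated cases will be conducted at the end of the study (after reaching the necessary number of cases"). The term validated is not defined.
- **7.9 (limitations).** "For those databases where free text is available (PHARMO, HSD, CPRD and SIDIAP), validation of endpoints will be conducted". There is no exemption for earlier validation, and Aarhus is not listed. The section then argues that, because cases and controls come from the same database, outcome misclassification is alike in both, so any bias merely varies from one database to another.
- **7.3.2 (outcomes, general).** Text searches for finding cases are confined to PHARMO because "free text does not add value or is absent/unavailable in the other databases". Tables 7-2 to 7-4 likewise show text for PHARMO only. Laboratory values serve to verify diagnoses, "which may be used in sensitivity analyses (e.g. any case, laboratory confirmed cases only").

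**The concern.** A database drops out of validation under 7.3.2.1 to 7.3.2.3 for either of two reasons: validation is not feasible there, or the outcome was validated there before. An earlier validation yields an average PPV for some algorithm in some earlier population. It removes no false positive from this study's case series. It may not even describe the algorithm used here, because 7.3.2.1 and 7.3.2.2 say database-specific algorithms are still to be developed, and 7.6 allows codes to be updated during the project.

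Section 7.9's reassurance does not help. False positives sit among the cases by construction, and drawing controls from the same database does not take them out. Section 7.9 acknowledges attenuation for missed LCZ696 exposure but gives no direction for misclassified outcomes.

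The direction matters because section 7.5 aims to show that the risk is below 3-fold (hepatotoxicity) or 5-fold (myotoxicity, acute pancreatitis). Dilution toward 1 makes that easier to show when it is false. The definition also decides when the final analysis may start, since 7.7.2 ties it to reaching the required number of cases: 40 recorded cases at a PPV of 0.8 contain 40 × 0.8 = 32 true ones.

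**Working it through.** **Inputs from section 7.5:** margins 3 and 5; one-sided 5% error; 80% power; 1:4 matching; LCZ696 use in controls p0 = 0.20. **Assumed, because the protocol gives no value:** the PPV, the share of cases from exempt databases, and false positives exposed like controls.

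**Step 1: reproduce Table 7-6.** With a true OR of 1,

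n cases = (1.645 + 0.842)² / ln(margin)² × (1 + 1/4) / [p0(1 − p0)].

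- Margin 3, 20% use: 40.02 (stated 40).
- Margin 5, 20% use: 18.65 (stated 19).
- The other entries give 33.15, 71.15, 178.72 and 100.53 (stated 33, 71, 179 and 100).

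The table is right on its own terms, which treat every counted case as a true case.

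**Step 2: exposure among true cases.** p1 = OR × 0.25 / (1 + OR × 0.25), which is 0.4286 for a true OR of 3 and 0.5556 for a true OR of 5.

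**Step 3: exposure among recorded cases.** pm = PPV × p1 + (1 − PPV) × 0.20, and observed OR = [pm / (1 − pm)] / 0.25. At PPV 0.8 and true OR 3: pm = 0.8 × 0.4286 + 0.2 × 0.20 = 0.3829, so the OR is 2.48.

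**Step 4: chance of wrongly ruling out the margin when the true OR equals it.** SE = √(1/[n·pm(1 − pm)] + 1/[4n·p0(1 − p0)]), and the chance is Φ((ln margin − ln observed OR)/SE − 1.645). At PPV 0.8 and n = 40: SE = √(0.1058 + 0.0391) = 0.381, and Φ(0.499 − 1.645) = 12.6%.

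| Overall PPV | True OR 3 seen as | False rule-out, 40 cases | True OR 5 seen as | False rule-out, 19 cases |
|---|---|---|---|---|
| 1.0 | 3.00 | 5.0% | 5.00 | 5.0% |
| 0.95 | 2.86 | 6.4% | 4.65 | 6.5% |
| 0.9 | 2.73 | 8.1% | 4.33 | 8.4% |
| 0.8 | 2.48 | 12.6% | 3.76 | 13.2% |

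An unmatched simulation with 200,000 runs gives 4.4%, 7.4% and 11.5% at PPV 1.0, 0.9 and 0.8 for 40 cases, and 5.1%, 8.4% and 13.2% for 19 cases.

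**Step 5: only some cases unconfirmed.** If a share f of cases is unconfirmed with PPV q, and the rest are all true, the overall PPV is 1 − f(1 − q). With q = 0.8, a quarter unconfirmed gives 0.95, half gives 0.9 and all gives 0.8, so the table covers these mixtures.

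**Step 6: does the direction hold?** At PPV 0.8 and true OR 3, false positives exposed at 20% give 2.48, at 43% give 3.00 (no dilution), at 50% give 3.18 and at 60% give 3.45. With a true OR of 1, false positives exposed at 30% give 1.13. The move toward 1 is therefore conditional.

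**The case against.** Four objections carry weight.

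- **Validated may refer to the outcome, not the case.** The exemption speaks of outcomes validated within a database. Cases found by an already validated algorithm could then count as validated, and 7.7.2 would largely agree with 7.3.2.1 to 7.3.2.3. The protocol does not say so, and this reading still leaves out databases where validation is not feasible. The ambiguity stands.
- **Section 7.9 may govern.** Four of five databases would then validate, and the unconfirmed share could be small. It might also be said that 7.3.2 restricts text only for finding cases, not for confirming them, and section 7.4.1 mentions text and original records in CPRD. But text that is absent cannot confirm a case either, and Tables 7-2 to 7-4 show none outside PHARMO. The sections still need reconciling.
- **A remedy is partly foreseen.** Section 7.3.2 names the contrast between any case and laboratory-confirmed cases, and 7.7.2.5 promises sensitivity analyses on the limitations in the SAP. This is fair, but 7.3.2 makes the contrast optional, and laboratory availability varies between databases (7.9).
- **The size is assumed.** This is correct. In addition, 7.7.2.3 reports 95% confidence intervals. If rule-out used their upper limit, the nominal error would be 2.5%, and PPVs of 0.9 to 0.7 would give about 4% to 11% for a true OR of 3.

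A reader might go further and infer that the OR will certainly be biased toward 1, that the exemption covers most databases for pancreatitis, or that exempt databases' cases will be dropped. The protocol supports none of these. It names no exempt database, does not say which databases took part in the earlier projects, and nowhere suggests dropping cases. The SmPC caution on statin co-administration (section 5) also makes closer attention to LCZ696 users plausible, which would work against dilution.

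**Conclusion.** The inconsistency is established from the text. The validation rules do not produce a case series validated at case level, section 7.9 states a different rule from 7.3.2.1 to 7.3.2.3, and its argument about matched cases and controls does not deal with false positives among the cases.

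The statistical consequence is conditional. If false positives have control-like LCZ696 use, an overall PPV of 0.95 to 0.8 raises the nominal 5% error of the rule-out to about 6% to 13%, for either margin. If earlier validations showed a high PPV, or few cases are unconfirmed, the effect is small. If LCZ696 users are coded preferentially, it can vanish or reverse. This should be repaired before the final analysis, but it is not evidence that the study's result will be wrong.

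**What to change.** 1. Reconcile 7.3.2, 7.3.2.1 to 7.3.2.3, 7.7.2 and 7.9: for each outcome, list which databases validate cases in this study, by what means, and which rely on earlier work.
2. State in 7.7.2 which cases count as validated and which count toward the 40 and 19. Do not describe cases from exempt databases as validated at case level.
3. Turn the optional contrast in 7.3.2 into a commitment: the pooled OR for individually confirmed cases (chart, text or laboratory) beside the pooled OR for all cases.
4. Add a quantitative bias analysis over the earlier PPVs and their uncertainty, as a sensitivity analysis only, because those PPVs come from other populations and perhaps other algorithms. Include scenarios with false positives exposed more often than controls.
5. Correct the statement in 7.9 on outcome misclassification: it should say that false-positive cases remain in the case series, and in which direction they may act.

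The cost is some added analysis, using validity data that the plan already intends to obtain for pancreatitis, and no new chart review. The confirmed-case estimate will be less precise and may rest on fewer than 40 or 19 cases. It should therefore qualify the rule-out conclusion and not act as a second mandatory test.

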7.3.2.2 Hepatotoxicity

Based on the level of elevation of transaminases or alkaline phosphatase (ALP) and the ratio (R) of elevation of baseline ALT to baseline ALP (ALT/ULN)/(ALP/ULN), drug-induced liver injury (DILI) is classified as either hepatocellular, cholestatic or mixed types (hepatocellular DILI: ALT \geq 3-times ULN and R \geq 5; cholestatic DILI: ALP \geq 2-times ULN and R \leq 2; mixed DILI: ALT > 3-times ULN and ALP > 2-times ULN and R > 2-times < 5-times ([Benichou 1990](#), [Devarbhavi 2012](#)). Not all the databases will allow for classification of the type of liver injury since ALT and ALP may not be available. Database specific algorithms based on codes, values and natural language processing (NLP) will be developed in line with the work done by [Overby et al \(2013\)](#) in the USA and [Afzal et al \(2013\)](#) in the Netherlands, where they explored various definitions of liver injury in electronic health care databases. [Table 7-3](#) shows the components that may be used for each of the databases. Viral hepatitis will be excluded from the cases.

For individual terms to identify cases with hepatotoxicity, see Annex 3 [Section 12.3.2.2](#).

Validation will be performed for all potential cases in the databases that allow for this and have not yet validated these outcomes.

Table 7-3 Components for the identification of hepatotoxicity by database

	Database (country)				
	PHARMO (NL)	HSD (IT)	Aarhus (DK)	CPRD (UK)	SIDIAP (ES)
Codes	ICPC/ICD-10	ICD-9	ICD-10	READ	ICD-9/10
Laboratory (ALT/ALP)	Yes	Yes	Yes	Yes	Yes
Text / symptoms	Yes	No	No	No	No

ALT = alanine aminotransferase; ALP = alkaline phosphatase; CPRD = Clinical Practice Research Datalink; DK = Denmark; ES = Spain; HSD = Health Search CSD Longitudinal Patient Database; ICD = International Classification of Diseases; ICPC = International Classification of Primary Care; IT = Italy; NL = the Netherlands; SIDIAP = Sistema d'Informació per al Desenvolupament de la Investigació en Atenció Primària; UK = United Kingdom

Note: details on databases, see [Section 7.4](#)

7.3.2.3 Acute pancreatitis

Acute pancreatitis is characterized by the onset of parenchymal and peripancreatic fat necrosis with associated inflammation in a previously healthy individual.

Acute pancreatitis describes an acute inflammatory process of the pancreas that rapidly depletes intravascular water and, if unchecked, promotes regional inflammation. Commonly accepted criteria for a clinical diagnosis of acute pancreatitis necessitate the presence of 2 of the 3 following features: serum amylase and lipase elevated at least 3-times ULN; characteristic epigastric abdominal pain; and typical radiologic features as found on computed tomography (CT), magnetic resonance imaging (MRI), or transabdominal ultrasound (US) ([Frossard 2008](#)). Acute pancreatitis has been investigated in several European multicenter database studies such as EU-ADR and SAFEGUARD, and the algorithms for identification of acute pancreatitis and the validity will be obtained from these consortia.

[Table 7-4](#) shows the components that may be used for each of the databases.

For individual terms to identify cases with acute pancreatitis, see Annex 3 [Section 12.3.2.3](#).

Validation will be performed for all potential cases in the databases that allow for this and have not yet validated these outcomes.

Table 7-4 Components for the identification of acute pancreatitis by database

	Database (country)				
	PHARMO (NL)	HSD (IT)	Aarhus (DK)	CPRD (UK)	SIDIAP (ES)
Codes	ICPC/ICD-10	ICD-9	ICD-10	READ	ICD-9/10
Laboratory (amylase/lipase)	Yes	Yes	Yes	Yes	Yes
Text / symptoms	Yes	No	No	No	No

CPRD = Clinical Practice Research Datalink; DK = Denmark; HSD = Health Search CSD Longitudinal Patient Database; ES = Spain; ICD = International Classification of Diseases; ICPC = International Classification of Primary Care; IT = Italy; NL = the Netherlands SIDIAP = Sistema d'Informació per al Desenvolupament de la Investigació en Atenció Primària; UK = United Kingdom

Note: details on databases, see [Section 7.4](#)

7.3.3 Covariates

7.3.3.1 General

Co-variates are all variables which are associated with the specific outcome and those that may increase the systemic concentrations of statins. The latter will be assessed for all outcomes at the index date and comprise:

- Concomitant use of drugs potentially interacting with statins at the index date (current use at index date see [Section 7.3.1](#)):
 - Cytochrome P450 (CYP3A4) enzyme inhibitors (particularly important for the CYP3A4 substrates simvastatin, lovastatin, and atorvastatin), e.g. diltiazem, verapamil, clarithromycin, telithromycin, erythromycin, itraconazole, cyclosporine, protease inhibitors (ritonavir, indinavir, and saquinavir), amiodarone, and fusidic acid
 - CYP2C9 enzyme inhibitors (with effects on fluvastatin, a CYP2C9 substrate): e.g. omeprazole, fluconazole
 - OATP1B1 inhibition (with effects on atorvastatin, simvastatin, pravastatin, lovastatin, and rosuvastatin): e.g. gemfibrozil

Complete lists for these interacting drugs will be described in the statistical analysis plan (SAP) based on resources from prior studies and relevant open source databases.

In addition, we will look at covariates that will be associated with statin use and proxies for HF severity in all analyses.

- Number of statin prescriptions in the year prior to index date
- Number of different ATC codes in the year prior to index date
- Comorbidities (i.e. diseases/conditions already prevalent at the index date or which occurred or were recorded within 12 months prior to the index date), e.g.
 - Hypertension
 - Myocardial infarction
 - Stroke
 - Angina pectoris
 - Atrial fibrillation
 - Valvular disease
 - Diabetes mellitus
 - Respiratory disease (asthma, chronic obstructive pulmonary disease [COPD])
- Comedication at the index date, e.g.:
 - ACEIs and/or ARBs
 - Beta-blockers
 - Calcium channel blockers
 - Mineralocorticoid receptor antagonists (MRAs)
 - Diuretics (thiazides, loop, potassium-sparing diuretics, others [excluding MRAs])
 - Digoxin

- Nitrates
- Hydralazine
- Antiarrhythmic agents
- Anticoagulants
- Antiplatelets (including prescription aspirin)
- Lipid lowering drugs
- Antidiabetics

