7.3 Variables

7.3.1 Exposures of interest

Drug exposures of primary interest are statins and LCZ696. Information on these variables will be obtained from the prescription/dispensing files (for codes for statins, see Annex 3 Section 12.3.2, [Table 12-1](#)). The duration of each prescription/dispensing will be calculated by dividing the amount by the prescribed dose (if available) and otherwise by the national defined daily dose (DDD) equivalent. Exposure to LCZ696 will be assessed at the index date (date of outcome of interest) and categorized in the following categories of recency of use:

- Current use: the prescription duration covers the index date or stops at most 7 days before
- Recent use: exposure ends between 8 and 90 days before the index date

For current users of LCZ696 at the index date, we will further classify the duration of exposure in the following categories:

- Short: Current use and initiated within past 30 days prior to index date
- Middle: Current use and initiated within past 31-90 days prior to index date
- Long: Current use and initiated more than 90 days prior to index date

For current users of statins, we will look at the daily dose in DDD equivalents for the statin component (see Annex 3, Section 12.3.3, [Table 12-1](#)) of the most recent prescription and categorize as:

- Low (< 1 DDD)
- Medium (1 DDD-1.5 DDD)
- High (> 1.5 DDD)

For the secondary analyses (see [Section 7.7.2.3](#)), the type of statin that is used closest to the index date will determine the type of statin.

Other exposures of interest will be drugs that may confound or modify the potential association; these are listed under the covariates (see [Section 7.3.3](#)). All drugs will be extracted on the basis of their ‘Anatomical Therapeutic Chemical’ (ATC) codes, and durations calculated as described above for the main exposures of interest.

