7.7.2.3 Primary and secondary analyses

Conditional logistic regression analyses will be used to estimate crude and adjusted relative risks (expressed as odds ratios [ORs]) of each specific outcome with corresponding 95% confidence intervals (CIs).

The primary analysis is current LCZ696 and statin versus current use of statin (any dose) without current use of LCZ696.

Secondary analyses comprise investigation of dose of statin and duration of LJC696, recent use of LJC696 or statins, and individual statins. In the dose specific analysis for statins the reference category will be current low dose of statins and non-use of LJC696.

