7.7.2.4 Confounding

Control for confounding will be based on matching and matched analyses plus adjustments based on the change in estimate method as proposed by [Maldonado and Greenland \(1993\)](#) per database.

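### As worded, the one-year ATC-code count in 7.3.3.1 includes LCZ696 itself, so adjusting for it can shift the LCZ696 odds ratio by the effect of one code

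*Protocol*

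**What the plan says.** Protocol 7.3.3.1 opens with a general definition: "Co-variates are all variables which are associated with the specific outcome and those that may increase the systemic concentrations of statins". After the interacting drugs it continues: "In addition, we will look at covariates that will be associated with statin use and proxies for HF severity in all analyses". The list that follows contains "Number of different ATC codes in the year prior to index date". The count carries no exclusion. The same list separately contains the number of statin prescriptions in the prior year, and ACEI/ARB use at the index date among the comedications.

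Protocol 7.3.1 defines the exposure window as "Current use: the prescription duration covers the index date or stops at most 7 days before" and says of drug coding: "All drugs will be extracted on the basis of their ‘Anatomical Therapeutic Chemical’ (ATC) codes".

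Protocol 7.7.2.3 sets the main contrast: "The primary analysis is current LCZ696 and statin versus current use of statin (any dose) without current use of LCZ696". Protocol 7.7.2.4 controls confounding by matching plus "adjustments based on the change in estimate method", applied per database.

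Protocol 7.7 announces a detailed SAP. Within 7.3.3.1, however, the explicit deferral to the SAP covers only the lists of interacting drugs. Sections 7.3.3.2 to 7.3.3.4 defer codes and algorithms for the outcome-specific covariates. Neither deferral mentions the ATC count.

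**The concern.** The count is meant to stand in for the patient's general drug burden and heart failure severity. A patient with current LCZ696 supply will normally have an LCZ696 prescription within the preceding year, so followed literally the count contains the exposure whose effect is being estimated.

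Take two patients with the same morbidity. One has 11 different codes in the year, including an ACEI/ARB, and has never had LCZ696: the count is 11. The other is identical but moved from the ACEI/ARB to LCZ696 four months before index. Both the old and the new code fall in the year, so the count is 12. The extra unit reflects the exposure, not sicker health.

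If a higher count goes with a higher outcome risk, as one would expect of a severity proxy, the model credits that unit to severity and lowers the LCZ696 coefficient. The study aims to rule out 3-fold and 5-fold increases (7.5), so a downward shift is anti-conservative. The size of the artefact also depends on how recently LCZ696 was started, and duration of LCZ696 use is a secondary analysis.

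**Working it through.** **Inputs from the protocol.** Section 7.5: one-sided test, 5% type I error, 80% power, 1:4 case-control ratio, 20% LCZ696 use in controls (10% also tabulated); margin 3 with 40 cases for hepatotoxicity, margin 5 with 19 cases for myotoxicity and acute pancreatitis. The log odds ratio per ATC code, g, is not given. It is assumed below, with per-code odds ratios of 1.02, 1.05 and 1.10.

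**Step 1: the plan's own case numbers.** Non-inferiority on the log odds ratio with true OR = 1:

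cases = (1.645 + 0.842)² × (1 + 1/4) / [p(1-p)] / ln(margin)²

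| Margin | Computed, p = 20% | Table 7-6 | Computed, p = 10% | Table 7-6 |
|---|---|---|---|---|
| 5 | 18.65 | 19 | 33.15 | 33 |
| 3 | 40.02 | 40 | 71.15 | 71 |
| 2 | 100.53 | 100 | 178.72 | 179 |

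The table is reproduced to within rounding, so the formula gives the precision the plan assumes. With 40 cases, SE(log OR) = √[1.25 / (0.2 × 0.8) / 40] = 0.442. With 19 cases it is 0.641.

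**Step 2: the mechanical shift.** Let E be current LCZ696 use (0/1), b its log odds ratio, and let the total count be the other codes plus E. Then

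b·E + g·(other codes) = (b - g)·E + g·(total count).

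Adjusting for the total count therefore estimates b - g, and the adjusted OR equals the intended OR × exp(-g).

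**Step 3: size.** The error of wrongly ruling out the margin when the true OR equals it is Φ(-1.645 + g/SE), using the plan's SE.

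| Per-code OR (assumed) | g | Factor exp(-g) | Target when true OR is 3 | Error, margin 3, 40 cases | Error, margin 5, 19 cases |
|---|---|---|---|---|---|
| 1.00 | 0 | 1.00 | 3.00 | 5.0% | 5.0% |
| 1.02 | 0.020 | 0.98 | 2.94 | 5.5% | 5.3% |
| 1.05 | 0.049 | 0.95 | 2.86 | 6.2% | 5.8% |
| 1.10 | 0.095 | 0.91 | 2.73 | 7.6% | 6.7% |

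If the SE is evaluated at an OR of 3 instead (0.376 with 40 cases), the margin-3 errors are 5.6%, 6.5% and 8.2%.

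**Step 4: who is affected.** Simulated 1:4 case-control samples were fitted by ordinary logistic regression. True OR was 3 and per-code OR 1.10. Assumptions not in the protocol: a mean of 8 other codes, 85% ACEI/ARB use, and no effect of the ACEI/ARB code itself on the outcome.

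| Pattern | Count includes LCZ696 | Count excludes LCZ696 only | Count excludes LCZ696 and ACEI/ARB |
|---|---|---|---|
| LCZ696 added | 2.71 | 2.98 | 2.98 |
| Switch from ACEI/ARB within the year | 2.73 | 3.00 | 2.99 |
| Switch more than a year before index | 2.99 | 3.28 | 3.03 |

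The first two rows show the shift by exp(-g). In the third, the LCZ696 code takes the place of the ACEI/ARB code, so counting it does almost no harm, and removing LCZ696 alone biases upward. Removing both classes is close to 3 in every row. With a per-code OR of 1/1.05, the added-LCZ696 pattern gives 3.19 with LCZ696 counted and 3.04 without, an upward shift.

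**The case against.** The protocol never says in terms that LCZ696 is counted; this follows from the missing exclusion. The sentence on ATC extraction in 7.3.1 comes just after one about drugs other than the exposures of primary interest, so counting only other drugs is a possible reading. One drug source, CPRD, is coded in BNF/Multilex rather than ATC (Table 7-5), so an operational definition is needed anyway, and the SAP could supply the exclusion. This weakens any claim about what will be programmed. It does not change what the text says if followed as written.

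The covariate is only a candidate under change-in-estimate selection. With few cases spread over five databases it may not enter every model. No threshold is stated; under an assumed 10% cut-off, a shift of 2% to 9% would not by itself cause selection. That stands. But the mechanical shift is itself a change in estimate, so the rule offers no protection against it. With coarse categories instead of a linear count, the shift would be smaller and confined to patients near a cut-off.

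Other selected covariates would probably reduce the residual g. The reference group may include people who stopped LCZ696 within the year and also carry its code, which narrows the difference. Crude and adjusted ORs are both planned, so the joint effect of all adjustment will be visible, though not the part due to this count.

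A reader might infer that every current user, or at least everyone who started within 90 days, carries one surplus code. The documents do not support that: long-ago switchers do not, and a new LCZ696 starter compared with a new ACEI/ARB starter has no net extra code. Nothing in the protocol supports a scenario with two surplus codes, or larger per-code effects than those used here.

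**Conclusion.** The point holds as a conditional specification flaw. As worded, the covariate includes the exposure. The adjusted OR is multiplied by about 0.98 to 0.91, and the error of wrongly ruling out a 3-fold risk rises from 5.0% to about 5.5% to 7.6%, if four things hold: the covariate is selected, it enters roughly linearly, the per-code OR lies between 1.02 and 1.10, and current users mostly added LCZ696 or switched to it within the year. The log-scale shift of 0.02 to 0.10 is small beside an SE of 0.44 with 40 cases.

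It would be tempting to conclude that the study's adjusted ORs are biased downward as a matter of fact, or that its power calculation is wrong. Neither follows. The direction depends on the sign of g, which the protocol does not give; the share of long-ago switchers is unknown; and the case numbers in Table 7-6 are reproduced and unaffected. The flaw still merits correction, because in the more likely direction it favours a conclusion of safety and its size varies with time since LCZ696 was started.

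**What to change.** In 7.3.3.1, redefine the covariate as the number of different ATC codes in the year before the index date, leaving out LCZ696, ACEI/ARB and statin codes. The list of excluded codes should also cover fixed-dose combinations such as those in Table 12-1. Removing all three classes, rather than LCZ696 alone, makes the count independent of whether or when a patient switched. Little information is lost, because ACEI/ARB use at index and the number of statin prescriptions are already separate covariates. Reporting the LCZ696 OR with and without the count would show how much it matters.

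The cost is one phrase in the protocol and an exclusion list in the analysis script. No extra data are needed and no case number changes.
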